We propose a cluster randomized controlled trial to test the SPARK model of care for cancer inpatients in the acute hospital setting. This is novel in our institution because palliative care is currently delivered only as a separate consultation service – the most common model worldwide. (21) In the SPARK model, palliative care doctors and nurses are integrated with the oncology team, supporting them in their delivery of basic palliative care, seamlessly stepping in and out to deliver specialist palliative care directly to patients when needed. (22-25) With this approach, it is anticipated that there will be more efficient collaborative working between the oncology and palliative teams.

In the short term, our proposed study responds to an urgent need to expand access to palliative care for advanced cancer patients, in a model that does not require a large increase in specialist palliative care manpower. In the long term, scalable and effective models of care need to be developed for the exponentially rising need for palliative care in Singapore and across the world.

Methods

Study setting

The study will take place in Singapore General Hospital, a 1597-bedded acute hospital with more than 78,000 admissions per year. About 5,000 hospital admissions per year are cancer patients under the care of the Division of Medical Oncology (DMO), of which 80% are advanced cancer patients. This service is the largest public provider of cancer care in Singapore.

Current model of service

The current model of service is a consultation service with oncologist-driven referrals. A cancer patient admitted to hospital may have pain or other physical symptom problems such as breathlessness, or psychosocial and spiritual issues. The oncology team usually manages them first-line, and would refer to the palliative care team for further management only if the problems were unresolved after oncology management. Upon a referral from the oncologist, the palliative care team will review the patient and make suggestions for patient management, but the oncology team still takes primary responsibility for the patient's care. In the current model, about 20% of cancer inpatients are referred to the palliative care team.

The SPARK model of care

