Specific aim 3: A net cost analysis of SPARK will be undertaken from the perspective of the restructured health system. It is possible that total labour costs are greater for SPARK but that costs per patient are lower because SPARK allows for seeing more patients. This difference, whether positive or negative, represents differences in direct labour costs. Because this is a new model of care, this cost will not be reflected in the billing data. However, the billing data can be used to quantify other differences that may result from SPARK, such as savings through reductions in length of stay. Using the billing data, we will again quantify total and per capita cost differences between SPARK and usual care. The net costs of SPARK will be quantified by adding per capita labour cost differences to per capita billing cost differences. If negative, then SPARK is cost saving. If positive, then SPARK is more expensive.

Sample size calculation

It is estimated that each of the 4 clusters will have an average of 300 stage 4 cancer patient admissions per 4-month period, giving a total of 6000 admissions over the 20-month study period.

Based on results from our pilot study, we estimated the mean hospital length of stay to be about 6 days and the standard deviation to be 7. We estimated the intra-cluster coefficient arising from multiple admissions per person to be 0.2 and that each patient would have an average of 2 admissions during the study period. Therefore, the design effect arising from multiple admissions per person is 1.2 and 300 patient admissions would give an “effective sample size” of 250 admissions per 4-month period, or a total “effectiveness sample size” of 5000 admissions over the study period. Assuming the coefficient of variation between clusters to be about 0.25, the sample size of totally 6000 admissions as aforementioned would provide 80% power at 5% two-sided type 1 error rate to detect a mean difference of 1 day in hospital length of stay in the stepped-wedge design in table 1. (31)

References

1. WHO Definition of Palliative Care. <http://www.who.int/cancer/palliative/definition/en/> (last accessed 3 January 2017)

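### Aim 3 does not stop usual-care palliative consultations from being subtracted in both the labour and the billing terms of the net cost

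*Protocol*

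**What the plan says.** The net cost analysis is described only in the protocol, under Data analysis, Specific aim 3. The SAP covers Aims 1 and 2 and has no section on it.

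The protocol first compares labour costs under the two models: "This difference, whether positive or negative, represents differences in direct labour costs". It then explains why labour needs its own term: "Because this is a new model of care, this cost will not be reflected in the billing data". The billing data have a separate purpose: "However, the billing data can be used to quantify other differences that may result from SPARK, such as savings through reductions in length of stay". The billing comparison itself is: "Using the billing data, we will again quantify total and per capita cost differences between SPARK and usual care". No billed item is excluded. The two parts are combined as follows: "The net costs of SPARK will be quantified by adding per capita labour cost differences to per capita billing cost differences". The result is read by sign: "If negative, then SPARK is cost saving", and a positive result means SPARK is more expensive.

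Usual care is not free of palliative work. Under Current model of service, the protocol describes a referral-based consultation service and says that "about 20% of cancer inpatients are referred to the palliative care team". Neither document says whether those consultations are charged.

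**The concern.** The labour term is a difference, so it already subtracts the cost of usual-care palliative staff. The billing term is also a difference, taken over everything on the bill. The sum is valid only if palliative work is absent from the billing data in both conditions, or is removed from it. The protocol's reason for expecting its absence is novelty. That can hold for SPARK but not for a service already running.

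If usual-care consultations are charged and SPARK input is not, charges disappear from the bill when a team crosses over. The billing term counts that as a saving, although the labour term has already credited SPARK with the consultation labour it replaces.

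Lower net cost is one of the hypotheses in the protocol abstract, and the decision rule has no margin. An accounting artefact could therefore settle the conclusion when the true net cost is near zero.

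**Working it through.** The documents give no cost figure for Aim 3, so there is no stated result to reproduce. The check is an accounting identity per admission, with both per capita terms taken on that basis.

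**Inputs**
- U and S: palliative labour cost per admission under usual care and SPARK. Neither is given, so U is indexed at 100.
- O: difference in all other billed costs, set to 0 to isolate the effect.
- fB and fS: shares of usual-care and SPARK palliative labour that also appear on the bill. Aim 3 implies fS = 0. fB is not stated, so it is an assumption, varied from 0 to 1.
- Referral rate under usual care: about 20% (protocol, Current model of service).

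**Formulas**
- True net = (S − U) + O
- Planned net = (S − U) + (O + fS·S − fB·U)
- Error = planned − true = fS·S − fB·U
- With fS = 0, error = −fB·U, which is zero or negative and so favours SPARK.

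**Results with U = 100, O = 0, fS = 0**

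| fB | Planned net, S = 100 (true 0) | Planned net, S = 120 (true +20) |
|---|---|---|
| 0 | 0 | +20 |
| 0.25 | −25 | −5 |
| 0.50 | −50 | −30 |
| 0.75 | −75 | −55 |
| 1 | −100 | −80 |

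In the last column, planned net = 20 − 100·fB, so the sign turns negative once fB exceeds 0.20. That threshold follows from the chosen S and is unrelated to the 20% referral rate.

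**In terms of the charge.** Let c be the palliative charge per referred stay. Usual-care bills then contain 0.20c per admission on average. If SPARK bills contain none, error = 0 − 0.20c = −0.20c. If a proportion p of SPARK stays is billed at c, error = (p − 0.20)c. This is negative for p below 0.20, zero at 0.20 and positive above it.

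**If SPARK input is billed.** With S = U = 100 and fB = 0.5, fS = 0.5 gives 50 − 50 = 0, and fS = 1 gives 100 − 50 = +50. The error then runs against SPARK.

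**After the fix.** With palliative charges removed from both conditions, fB and fS no longer enter the billing term and the error is 0. A cost-neutral SPARK (S = U, O = 0) returns a net cost of 0.

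**The case against.** The strongest reply is that the key premise is missing. Neither document says that consultations are billed. If they are not, or if they are absorbed in a general ward charge, nothing is counted twice. This stands: a reader might infer that the planned sum does double count, and the documents do not support that. They show only that the plan leaves it possible.

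A second reply concerns wording. The cost said to be missing from the bills can be read as the labour difference between models, not SPARK's labour alone. The billing data are also reserved for other differences, with length of stay as the example, which suggests that palliative labour was meant to stay out. That is a fair reading of the intent. But novelty cannot keep an existing service's charges off the bill, and the next sentence takes the billing difference in total with no rule for exclusion.

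Third, a reader might infer that any error must favour SPARK. That holds only while SPARK input is unbilled. The protocol expects more patients to receive palliative input under SPARK, some of it direct care for complex problems. If such reviews are billed, the error can vanish or reverse.

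Fourth, it is tempting to express the shift in bed-days or as a fraction of the 1-day difference used in the sample size calculation. The documents give neither a consultation charge nor a bed-day charge, so such a figure would reflect only the assumed charge.

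Whether billed amounts should be re-expressed as unit costs is a separate preference and not part of this point.

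**Conclusion.** The point holds as a gap in specification, not as a demonstrated double count. Aim 3 adds a labour difference to an unfiltered billing difference, judges the result by sign, and justifies the separation with a reason that covers one model only.

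If usual-care consultations are billed and SPARK input is not, the sum is biased towards SPARK by 0.20 times the charge per referred stay. That rests on the protocol's approximate referral rate, which is given for cancer inpatients generally and is applied here to stage 4 admissions. The bias is zero if consultations are unbilled, and it reverses if more than about 20% of SPARK stays are billed at the same charge. Its size in money cannot be given. The index figures show only that a sign rule can be overturned, not that it will be.

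Net cost is not the primary outcome, and the length-of-stay analysis is unaffected. The change is still worth making, because the sign of this sum is the trial's stated test of whether SPARK saves money.

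**What to change.** In Aim 3, define the billing term as billing excluding palliative-care professional charges, in both usual-care and SPARK periods. State that palliative staff time is counted once, in the labour term, for both SPARK and the consultation service. State also whether usual-care consultations appear in the billing data.

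If palliative charges cannot be separated, say so and report net cost over a range of assumed billed shares for each model, using the error formula above.

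The cost is a little more analysis work and a few sentences in the protocol, repeated in the SAP, which has no text on Aim 3. The design and primary outcome do not change. If consultations prove to be unbilled and SPARK input is unbilled too, the exclusion alters nothing. The possible downside is that SPARK's net cost may look less favourable than under the present formula.

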The overall aim of this proposed study is to evaluate the impact of the Supportive and Palliative care Review Kit (SPARK) model of care compared to usual care on health services utilization, access to palliative care, net costs and the experiences of both patients and healthcare providers. SPARK is an integrated palliative care and medical oncology co-rounding model of care for cancer patients in the acute hospital setting. We plan to develop and comprehensively assess this model using a prospective cluster randomized controlled trial and semi-structured interviews.

The study specific aims and hypotheses are:

Specific aim 1: To determine the effectiveness of SPARK on hospital length of stay (primary outcome) and other health service utilization metrics

Hypothesis: The SPARK model of care will reduce hospital length of stay compared to usual care, due to earlier involvement of palliative care in the course of hospital admission and consequently swifter relief of problems that prompted the hospitalization.

Other metrics of health service utilization will also be explored, including hospital-free days and visits to the Emergency Department in the last 6 months of life, and number of days to hospital readmission within 30 days.

Specific aim 2: To assess the relationship between the SPARK model of care and access to palliative care services

Hypothesis: The SPARK model will be associated with a greater proportion of cancer patients who receive any form of palliative care input during their hospital admission.

Background and significance

Palliative care, according to the World Health Organization, is an approach that improves the quality of life of advanced cancer patients and their families, through early identification, assessment and treatment of pain and other problems, physical, psychosocial and spiritual. (1) Concurrent palliative care and oncology care for advanced cancer patients results in improved quality of life, better symptom control and perhaps even longer survival. (2-7) International organizations recommend that palliative care should be integrated with oncology – the question that remains is how this integration should occur to optimize health outcomes. (7-9)

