Patient quality of life, measured by patient questionnaires, will not be measured because this was found to be infeasible in our pilot study. In the inpatient hospital setting, patients were physically ill with acute problems such as pain, leading to low recruitment and data completion rate.

Specific aim 1: To analyze the effect of the SPARK model on hospital length of stay and health services utilization. The following data will be extracted from the electronic health records: dates of hospital admission and discharge for the index admission and all subsequent admissions, dates of all subsequent Emergency Department attendances, and date of referral to community palliative care services.

Specific aim 2: To determine the access to palliative care. The receipt of different forms of palliative care from the palliative care doctor/nurse will be recorded. This may include direct care as well as indirect input e.g. specific advice regarding medication dose for that particular patient or suggestion of an appropriate source of support in the community for the patient.

Data analysis

Specific aims 1 and 2: Mixed-effect linear regression will be used to compare differences in (log-transformed) length of stay (primary outcome) and hospital-free days in the last 6 months of life between 'spark intervention' and 'usual care' groups controlling for (team- and patient-level) clustering and time effect. (30) Similarly, mixed-effect logistic regression will be used to compare the proportion of patients who receive direct palliative care in the usual care model versus the SPARK model. A separate analysis will also be done for patients who receive any specific form of palliative care (direct or indirect).

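### Aim 3 reads SPARK as cost saving or more expensive from the sign of a summed per capita difference, with no time or team adjustment, no interval, and *per capita* left undefined

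*Protocol*

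**What the plan says.** Cost is part of the trial's purpose. The overall aim in the Protocol (Specific aims and hypotheses) covers "health services utilization, access to palliative care, net costs and the experiences of both patients and healthcare providers", and the Abstract hypothesises a lower net cost under SPARK. That section then numbers only aims 1 and 2. Aim 3 appears for the first time under Data analysis.

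That one paragraph is the whole cost plan:

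- Labour: total labour cost may rise, yet it is possible that "costs per patient are lower because SPARK allows for seeing more patients".
- Billing: "we will again quantify total and per capita cost differences between SPARK and usual care".
- Combination: "The net costs of SPARK will be quantified by adding per capita labour cost differences to per capita billing cost differences".
- Interpretation: "If negative, then SPARK is cost saving. If positive, then SPARK is more expensive".

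The analysis that controls for team, patient and time opens "Specific aims 1 and 2: Mixed-effect linear regression will be used to compare differences", in both the Protocol and the SAP. The SAP contains no cost analysis. The data lists in both documents cover aims 1 and 2, and name no billing or labour fields.

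**The concern.** In a stepped-wedge trial the treatment comparison is tied to calendar time. Every team starts in usual care and ends in SPARK, so a comparison that ignores period mixes the effect of SPARK with any drift in cost. The teams also spend unequal time in each condition, so a comparison that ignores team picks up whatever cost differences exist between them. The plan guards against both for length of stay and for access to palliative care. It states no such protection for cost.

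No measure of uncertainty is planned either, so nothing in the procedure can return an inconclusive answer. SPARK adds a palliative care physician and a nurse to the team. The cost conclusion therefore turns on whether billing savings offset a labour difference, and the size and even the sign of that difference can depend on what it is divided by. With *per capita* undefined, that choice could be made after the data are seen.

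**Working it through.** **Reproducing the plan's own figure.** The documents give no mean, SD or trend for cost, so the only figure to check against is the power for length of stay. Inputs from Sample size calculation: 4 teams, 5 periods, 300 admissions per team-period, design effect 1.2 (so 300/1.2 = 250 effective), mean 6 days, SD 7, and "Assuming the coefficient of variation between clusters to be about 0.25", so τ = 0.25 × 6 = 1.5 days.

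For a random team intercept and fixed period effects, the variance of the SPARK effect is

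I·s²(s² + T·τ²) / [(I·U − W)s² + (U² + I·T·U − T·W − I·V)τ²],

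with I = 4 and T = 5. From Table 1, U = 10 (SPARK cells), W = 30 (sum of squared column totals) and V = 30 (sum of squared row totals). The cell variance is s² = 49/250 = 0.196.

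- Numerator: 4 × 0.196 × (0.196 + 11.25) = 8.974
- Denominator: 10 × 0.196 + 30 × 2.25 = 69.46
- Variance 0.1292, SE 0.359 day
- Power for 1 day: Φ(1/0.359 − 1.96) = 79.5%, which matches the stated 80%

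**Time.** Usual-care cells in periods 1 to 5 number 4, 3, 2, 1, 0, so their mean period is (4×1 + 3×2 + 2×3 + 1×4)/10 = 2.0. SPARK cells number 0, 1, 2, 3, 4, so their mean period is (1×2 + 2×3 + 3×4 + 4×5)/10 = 4.0. The gap is 2 periods, or 8 months. The yearly cost trend is an assumption:

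- +2%: 1.02^(8/12) − 1 = +1.3%; +5%: +3.3%
- −2%: −1.3%; −5%: −3.4%

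**Team.** Teams 1 to 4 supply 4, 3, 2, 1 SPARK cells and 1, 2, 3, 4 usual-care cells. With equal cell sizes, a crude difference weights them (4−1)/10, (3−2)/10, (2−3)/10, (1−4)/10 = +0.3, +0.1, −0.1, −0.3. The squared weights sum to 0.20.

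**Precision.** Assumption: cost per admission varies like length of stay, relative to its mean. Labour is treated as known without error.

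- Crude variance = 0.20τ² + (1/10 + 1/10) × 0.196 = 0.20τ² + 0.0392
- Adjusted variance = the formula above
- 95% half-width = 1.96 × SE / 6

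| Between-team CV | τ (days) | Crude SE | Crude 95% | Between-team share of crude variance | Adjusted SE | Adjusted 95% |
|---|---|---|---|---|---|---|
| 0.05 | 0.30 | 0.239 | ±7.8% | 31% | 0.330 | ±10.8% |
| 0.10 | 0.60 | 0.333 | ±10.9% | 65% | 0.350 | ±11.4% |
| 0.25 | 1.50 | 0.699 | ±22.8% | 92% | 0.359 | ±11.7% |
| 0.40 | 2.40 | 1.091 | ±35.7% | 97% | 0.361 | ±11.8% |

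The adjusted interval barely depends on the unknown team variation. The crude one depends on it heavily, and its half-width leaves out the trend shift.

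If the within-cluster SD were 1.5 or 2 times as large (at CV 0.25), the adjusted SE would be 0.536 or 0.708 day, giving ±17.5% or ±23.1%. With t multipliers on the SE of 0.359/6 = 6.0%: 11 df (20 cells − 5 periods − 3 teams − 1 effect) gives 2.20 × 6.0% = ±13.2%, and 2 df (4 teams − 2) gives 4.30 × 6.0% = ±25.8%.

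**Why the denominator needs stating.** Under usual care "about 20% of cancer inpatients are referred to the palliative care team". Let usual-care labour cost be c per admitted patient, hence c/0.20 = 5c per patient seen. Assume equal admissions in each condition, a share p seen under SPARK, and total labour cost multiplied by k. Take k = 1.5 and p = 0.40, both assumptions:

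- Per patient seen: 1.5c/0.40 − 5c = −1.25c, a fall of 25%
- Per admitted patient: 1.5c − c = +0.5c, a rise of 50%

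The signs differ whenever 1 < k < p/0.20, that is for k up to 1.5, 2 or 3 at p = 0.30, 0.40 or 0.60.

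**The case against.** Several points on the other side are sound.

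- **The denominator.** A reader might infer that labour will be divided by patients seen and billing by patients admitted. The documents do not show this. Both components are called per capita, and the word *again* in the billing sentence ("we will again quantify total and per capita cost differences between SPARK and usual care") suggests the same quantities as for labour. The Protocol also counts indirect input as palliative care, so seeing more patients need not mean direct consultations only. What is established is that the term is undefined. The arithmetic above shows why a definition matters; it does not show a mismatch.
- **Team imbalance.** A reader might call this bias. Crossover timing is randomised, so it is chance error with expectation zero. Nor does adjustment always narrow the interval: at a coefficient of variation of 0.05 or 0.10 the crude interval is the narrower one. The value 0.25 was assumed for length of stay, and quoting ±23% or a 92% between-team share as the result for cost would rest on that one borrowed number.
- **Time.** The trend shift is modest under the assumed 2% to 5% a year. It is still systematic, because SPARK follows usual care in every team however the order is drawn.
- **The sign sentences.** They may only explain a sign convention. On that reading, too, no interval is planned. That an unbiased symmetric estimate is negative half the time at a true zero holds for any trial and says nothing specific against this one.
- **Abridgement.** The aim 3 text may have been shortened: it refers to a difference that has not been introduced. A fuller cost plan could exist, but neither document contains or cites one.

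**Conclusion.** The concern holds as a gap in the plan for a stated, non-primary hypothesis. Neither document specifies a time or team adjustment, an interval or a definition of *per capita* for aim 3, yet the Protocol says how the sign of the result is to be read.

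The 8-month offset and the team weights follow from Table 1, with equal cell sizes. The percentages do not: the shift of 1.3% to 3.4% needs an assumed trend, and the intervals of ±8% to ±36% crude and ±11% to ±12% adjusted need cost to vary like length of stay. A larger cost SD or a small-sample correction widens the adjusted interval to between ±13% and ±26%. The case for adjustment is that it removes the common trend and makes precision nearly independent of the unknown team variation.

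A reader might go further and conclude that the cost result will be wrong, or that a crude analysis is intended. The documents support neither. They leave the estimator open, and the size of any error cannot be known from them. The primary analysis and the sample size are not affected.

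**What to change.** Add an aim 3 section to the SAP that does the following.

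1. Defines one denominator for both labour and billing costs, for example all eligible stage 4 admissions under each condition. If patients are used instead, state how those with admissions under both conditions are assigned, since the plan expects an average of 2 admissions each.
2. Estimates the billing difference on the arithmetic-mean scale, with period fixed effects and team and patient effects. A log-scale contrast, as planned for length of stay, could not be added to a labour cost.
3. Adds the labour difference on the same denominator, with a sensitivity range.
4. Reports net cost with a 95% interval suited to 4 clusters.
5. Rewords the two sign sentences so that the sign describes the point estimate and the conclusion reflects the interval. A rule that permits a label only when the interval excludes zero is not required.
6. Names the billing and labour fields to be extracted.

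The cost is a short SAP section, one further model on billing data the Protocol already intends to use, and a labour-cost input. Design and enrolment do not change. The downside is a little more analysis work and a cost result that may be inconclusive.
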